## Executive summary

---

The overall goal of this project is to investigate the effectiveness of a universal, mental health promotion and suicide prevention program – Youth Aware of Mental Health (YAM) – for reducing suicidal ideation and behaviour (attempts and deaths) and increasing help-seeking. YAM is a universal evidence-based mental health promotion program for 14- to 16-year-olds. YAM was developed for the Saving and Empowering Young Lives in Europe (SEYLE) study, a multicentre, cluster-randomised controlled trial involving 11,110 adolescent students with a median age of 15 years, recruited from 168 schools in ten European Union countries. In the European trial, YAM was shown to reduce depression and anxiety, suicide attempts, and severe suicidal ideation and facilitated healthy lifestyle choices among young people.

The YAM program will be offered to all Year 9 students in government and non-government ACT schools. Students from participating schools are being invited to participate in an evaluation of YAM – a waitlist-controlled trial commencing Term 2 to Term 4, 2020. Data will be collected at baseline, immediate post, and 3-month follow-up.

## 1. Introduction

---

### 1.1 Background and rationale

Young people can be particularly vulnerable to mental health problems, self-harm and suicide. Schools offer an ideal environment in which to implement suicide prevention initiatives for reaching young people. Although there is no direct evidence that school-based programs prevent suicide deaths, they have been shown to improve student knowledge and attitudes toward suicide and, in some cases, to reduce suicidal ideation and suicide attempts. Based on a thorough review of the literature, only a few school-based programs were identified that had shown significant positive effects on suicidal behaviours, suicide literacy, and/or protective factors for suicide such as help-seeking behaviour. The programs that were identified are:

- Youth Aware of Mental Health (YAM)
- Signs of Suicide
- Sources of Strength

All three programs are supported by RCT evaluation results, with YAM and Signs of Suicide demonstrating reductions in suicidal behaviours among young people, and Sources of Strength showing increased help-seeking behaviour and improved acceptability of help seeking. As the primary outcome of the broader LifeSpan suicide prevention trial is to achieve reductions in either suicide mortality rates and/or suicide attempts, it was decided to focus on the two programs which had an evidence-base for reducing suicide behavioural outcomes: YAM and Signs of Suicide. Based on the strength of the research evaluation design, the YAM program was selected as the school-based program for the LifeSpan trial. This YAM program and its efficacy are described below.

#### **Youth Aware of Mental Health**

The Youth Aware of Mental Health (YAM) program is a universal intervention that aims to raise mental health awareness about risk and protective factors associated with suicide (including knowledge about depression and anxiety), and to enhance the skills needed to deal with adverse life events, stress, and suicidal behaviours. It incorporates (i) three hours of role-play sessions with interactive workshops, (ii) a 32-page booklet for students to keep, (iii) six educational posters displayed in each participating classroom, and (iv) two 1-hour interactive lectures about mental health at the beginning and end of the intervention.

YAM was developed for the Saving and Empowering Young Lives in Europe (SEYLE) study, a multicentre, cluster-randomised controlled trial involving 11,110 adolescent pupils with a median age of 15 years, recruited from 168 schools in ten European Union countries. Schools were randomly assigned to one of three interventions or a control group. The interventions were:

1. Question, Persuade, Refer (QPR): a gatekeeper training module targeting teachers and other school personnel
2. YAM: a schools-based program targeting adolescent students, and
3. Screening by professionals (ProfScreen) with referral of at-risk students.

The primary outcome measure was the number of new suicide attempts made at the 3-month and 12-month follow-up. No significant differences were observed between the intervention and control conditions at the 3-month follow-up. At the 12-month follow-up, YAM was associated with significantly fewer incident suicide attempts, i.e., new cases of suicide attempts identified at either the 3-month or 12-month follow-up (odds ratios [OR] 0.45, 95% CI 0.24-0.85;  $p=0.014$ ), as well as a significant reduction in severe suicidal ideation (0.50, 0.27-0.92;  $p=0.025$ ) compared with the control condition. Fourteen students (0.7%) reported incident suicide attempts at the 12-month follow-up in the YAM condition compared with 34 (1.51%) in the control condition, while 15 students (0.75%) reported incident severe suicidal ideation in the YAM condition compared with 31 (1.37%) in the control condition. The YAM intervention showed an absolute risk reduction of approximately 1% when the two outcomes of suicidal ideation and attempt were combined, which equated to one suicidal outcome being prevented for approximately every 91 students exposed to the YAM intervention. No participants died by suicide during the study period.

## 1.2 Objectives

The primary aim of the YAM study is to determine whether there is a significant decrease in suicidal ideation severity across time (from immediate post-intervention and 3-month follow-up, compared to baseline) compared to a waitlist control group.

The study also aims to determine whether students receiving YAM compared to students receiving classes as usual (the waitlist control group), will have reported:

- a) Reduction in the rate of self-harm at 3-month follow-up;
- b) Increase in help-seeking intentions for suicide immediately post-intervention and 3-month follow-up;
- c) Increase in help-seeking behaviour for suicide immediately post-intervention and 3-month follow-up;
- d) Decrease in suicide stigma immediately post-intervention and 3-month follow-up;
- e) Increase in suicide literacy immediately post-intervention and 3-month follow-up;
- f) Decrease in depression symptoms immediately post-intervention and 3-month follow-up;
- g) Decrease in loneliness immediately post-intervention and 3-month follow-up;
- h) Increase in confidence supporting peers immediately post-intervention and 3-month follow-up;
- i) Increase in mental wellbeing immediately post-intervention and 3-month follow-up.

Process outcomes for the implementation of the YAM intervention in the ACT will also be evaluated; including:

- a) Number of schools contacted and signed on for participation in the YAM program;
- b) Number of Instructors and Helpers trained to deliver YAM;
- c) Number of schools that completed the YAM program;
- d) The extent to which the program was delivered as prescribed;

### 1.3 Hypotheses

Immediately post-intervention and at 3-month follow-up, relative to baseline, it is hypothesised that student participants that have received the YAM intervention will report:

1. decreased suicidal ideation severity compared to control
2. greater reduction in rates rate of self-harm compared to control
3. greater increase in help-seeking intentions for suicide compared to control
4. greater increase in help-seeking behaviour compared to control
5. greater reduction in stigma relating to suicide compared to control
6. greater increase in knowledge relating to suicide compared to control
7. greater reduction in depression symptom severity compared to control
8. greater reduction in loneliness compared to control
9. greater increase in confidence supporting peers compared to control
10. greater increase in mental wellbeing compared to control

### 1.4 Trial design

YAM will be evaluated using a randomised waitlist-controlled design. All Education Directorate (government) mainstream secondary schools and all Independent and Catholic schools will be invited to trial YAM through an expression of interest process. The active intervention will take place over a 12-month period, beginning Term 2 2020. Data will be collected via student self-report (Appendix A). Measurement of primary and secondary outcomes will be taken at three time-points: pre-intervention (baseline), immediate post-intervention, and at 3-month follow-up. Parent/guardian consent will be sought for students to participate in the data collection.

**Table 1.** Trial design and data collection timeline

	May-Jul T2	May-Jul T2	May-Jul T2	Aug-Oct T3	Oct-Dec T4
Cluster A schools	Pre-survey	YAM	Immediate post-survey	3-month post-survey	usual classes
Cluster B schools	Pre-survey	usual classes	Immediate post-survey	3-month post-survey	YAM

### 1.5 Procedure

*Cluster A schools:*

Consenting schools will be randomly allocated to the intervention or waitlist arm via cluster randomisation. Students in Cluster A schools will complete a baseline survey before participating in the YAM program and immediate post survey after program completion, all occurring in Term 2, 2020. They will then complete a 3-month post survey in Term 3, 2020.

*Cluster B schools:*

Surveys will be administered at the same time for students in Cluster B schools, but instead of receiving the YAM program in Term 2, 2020, they will have classes as usual. These students will receive YAM in Term 4, 2020.

If there are schools receiving the YAM program in Term 3, 2020 we aim to invite them to participate in the study as additional data would be valuable. These schools would administer surveys at pre- and post-YAM only, within Term 3.

The survey will take approximately 30 minutes to complete. All data will be securely stored at the Black Dog Institute, UNSW, with access to the data restricted to trial personnel and investigators.

### **Supervision of in-class surveys**

Completion of the in-class surveys for all schools will be supervised by Black Dog Institute volunteer research assistants in addition to a school contact nominated by the Principal. These research assistants will be recruited and trained specifically for this study and valid Working With Vulnerable People registrations will be sent through to HREC once they are recruited. Applicants with a background in psychology, mental health, education, teaching, youth work, or counselling will be preferenced. As these individuals are recruited into the project, Personnel Modification requests will be submitted to UNSW HREC. Successful applicants will be required to attend a one day face-to-face training workshop at Australian National University (partner university on this project) in which they will learn about our Research Codes of Conduct, as well as student welfare management, risk flagging, and what to do when a young person discloses something to them that concerns the safety of themselves or someone else. All volunteer research assistants will be provided with a step-by-step guide in how to manage interactions and what to communicate with participants. All research assistants will adhere to a field work protocol developed for the study, as is the Black Dog Institute standard practice. This protocol will include step-by-step instructions for each activity to be completed before, during and after the visit, details about how to check in/out of their visit by communicating with Black Dog research staff, and a checklist of materials required at each visit.

### **Program fidelity**

Assessing treatment fidelity is a core methodological consideration in the study of treatment outcome; it influences both the degree to which changes can be attributed to the intervention and the ability to replicate and disseminate the intervention. Treatment fidelity refers to the degree to which a treatment or intervention is delivered as prescribed and is critical to successful translation of evidence-based interventions into practice. Many studies have attempted to specifically evaluate the association of treatment fidelity and outcome with varying results. We will evaluate the degree to which YAM has been delivered across schools as intended within a large suicide prevention research trial, by assessing various aspects of fidelity. We will also evaluate whether treatment fidelity may influence effectiveness of the program outcomes.

YAM Instructors and Helpers, who are involved in delivering the program, are expected to complete an online survey immediately after the last session of YAM within the school, as a standard requirement of program delivery. We will be asking YAM Instructors and Helpers if they consent for the information they provide on these online surveys to be used for research purposes. That is, we will be adding a participant information and consent section to their pre-existing program fidelity feedback form.

## **1.6 Significance**

LifeSpan represents an opportunity to contribute to the presently sparse evidence base for suicide prevention programs in Australian schools. There is a strong need for such research, given the high prevalence of suicidal behaviours in Australian youth, the significant burden associated with suicide, and the pressure placed on governments from the community to act to prevent youth suicide. The delivery of YAM as a part of this trial has the potential to significantly impact the suicide rate of young Australians, as well as stimulate more high-quality research in this critical area.

## 2. Methods: Participants, interventions, and outcomes

---

### 2.1 Study setting and recruitment method

The Principal of eligible schools will be approached in the first instance by the ACT Health Suicide Prevention Officer who will meet with the school to explain the delivery and evaluation procedure. The Principal will be emailed a brief study invitation cover letter, study timeline (Appendix B), School Information Booklet outlining important details about the study (Appendix C) and a letter of support template (Appendix D). Principals will be instructed to contact the research team if they are interested in taking part. A week after sending these emails, a member of the research team will follow up with these schools via email or phone to confirm that they received the information and to enquire about whether they would like their school to take part. Schools will have the opportunity to hear more information over the phone or to arrange a face-to-face consultation with the research team. Those who wish to take part will be instructed to sign and return the letter of support. After the letter of support has been signed and returned, a meeting (either face to face or over the phone) will be planned with the team to make decisions regarding timetabling and trial administration processes for the school.

Recruitment will occur at the school level and therefore we will not be recruiting students or parents directly into the study. After the school has consented to participate, parents and students will be informed of the study in a variety of ways:

- (a) Via a 'parent information session' – If possible and supported by the school, a parent information session at the school will be arranged. This may be a standalone session dedicated to giving parents and students information about the study. Alternatively, information about the study may be announced as part of an existing school event. At these events, parents and students will be given the opportunity to ask questions. Here, the Parent Information Consent Form (Appendix E) will be distributed.
- (b) Via newsletters - Schools may also choose to circulate an information sheet via their standard school newsletters to inform parents and students about the upcoming study (Appendix F).
- (c) Via the information and consent form - If routes (a) or (b) are not taken, parents and students will be first notified of the study when the information and consent forms are distributed as part of the consent process outlined in section 2.2.

### 2.2 Consent process

Schools: Consent for the participation of the school will first be sought via a signed letter of approval from the school Principal.

Parents: Parental consent will be obtained before student consent. We will primarily seek consent via an electronic study invitation sent by the school. Parents will be asked to make a choice whether or not they would like to participate and submit their response to the research team via an online form. This ensures there will be no follow-up with parents who do not wish for their child to participate. Verbal consent will be offered to those parents who fail to respond to the initial consent via electronic means after two weeks, in order to allow for more complete and inclusive participation in the study. Details about the consent process for parents are provided below:

- School portal/app – Where available, a study invitation will be distributed via the school portal or app (e.g., SkoolBag, EdSmart, Moodle or other platforms used by schools).

This will include a URL link that will take parents to the information and consent section of the Black Dog Institute research platform. Here, parents and students can read information about the study, download a pdf copy of the information and parents can give their consent by filling in their details and submitting online. Parents who do not wish to consent will check the appropriate box and also submit the form online. Attached to these consent forms will be all information sheets, providing detailed information about the YAM program and the study. Parents will be instructed to discuss the study with their child to make sure they are informed and can reach a collaborative decision about whether to participate.

- Email – Where a school portal/app is not available or suitable, emails will be used to distribute the study invitation. Emails will be sent to parents of eligible students. These emails will similarly contain a link to the section of the Black Dog Institute research platform where they may read and download information forms and indicate consent via the online form.
- Phone calls – After 14 days following consent form distribution, follow-up phone calls will be made to parents who have not submitted a response via the online consent form. Phone calls will be made by a school staff member (where available and willing). The research team will collate the electronically submitted consent forms, then send a list of parents who have responded either yes or no to the study invitation, to the school staff member who will be conducting the follow-up phone calls. The staff member will be able to identify parents who are yet to respond based on school class lists. Administrative cost will be incurred by the project based on time spent at \$20/hour, for a maximum of 25 hours per school, pending SERAP and individual, school-level approval. The parent will be called, information about the study given to them verbally (see Appendix G for script), and verbal consent obtained. The staff member will log onto the Black Dog Institute research platform and enter the details of parents who give consent in this way. Parents may also choose to have the study invitation re-sent to them electronically if they wish.
- Renumeration – Parents will be informed that if they complete the consent form, whether it says 'yes' or 'no' to participation, their child will receive one entry into a draw to win a prize at the school (to be determined) valued up to \$30.

Students: Students will have been given information about the study via the parent information event, school newsletters, and/or the student information sheet provided to parents. A downloadable version of the Parent Information and Consent Form will be sent to parents, for students to also read and make an informed decision prior to the day of administration. Students whose parental consent has been confirmed will be taken through a Student Information and Consent Form (Appendix H) on the day of administration and required to tick and sign the relevant checkboxes and to indicate consent before beginning the survey. Students can choose not to participate in the study (even if their parents have provided consent).

YAM Instructors and Helpers: Opt-in consent will be obtained from YAM Instructors and Helpers via the pre-existing online survey, which will be prefaced with the research information statement and a consent check-box item with the response options: yes/no. This information and consent form will be downloadable.

Withdrawal of consent: If a parent, student, or YAM Instructor/Helper wishes to withdraw their consent during the study, they need to contact the research team (via [name]). No reasons need to be given. To do this, parents or students can download a copy of the withdrawal of consent form from the information and consent forms (Appendix I) and return this to the research team via email ([contact]) or mail (Black Dog Institute, [name]). A separate withdrawal of consent form will be available for YAM Instructor/Helpers with the same return process (Appendix J). Parents, students, or YAM Instructor/Helpers can also withdraw consent by [contact]). When a participant withdraws, they will be asked whether the study can retain their de-identified data up until that point. If they disagree, all data will be destroyed.

The consent forms will contain information on:

- The purpose and nature of the study;
- The study methods and what participation would involve;
- That participation is purely voluntary and that they are free to withdraw from the study at any time;
- That any decision they make about participation will not prejudice their future health care in any way;
- That their data will be kept strictly confidential in accordance with the relevant privacy legislation, used for health research only and will never be used in a way which would identify them personally;
- That they will not receive any individual feedback about any aspect of their data;
- That the research has been approved by the appropriate Research Ethics Committee and that all research carried out within the study will conform to strict ethical guidelines.

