#### **4.3 Students identified to be at immediate risk of suicide or other harm**

Student surveys will be confidentially viewed within 24 hours of completion by the research team as part of the monitoring and referral process to identify 'at-risk' respondents. Students who endorse any of the suicidal ideation or self-harm questions will be 'flagged' (specific criteria below) and the school Principal will be notified to coordinate follow up with these students by the school's wellbeing team in accordance with usual school procedures. The selection of these items has been made in consultation with the ACT YAM working group, ACT health and ACT Education Directorate. The research team will prepare the school Principal of this process ahead of time. Students will be notified of this referral process prior to them completing the questionnaire.

There are nine items for students will be flagged. A student will be flagged if they select the any of the following responses for:

- i) Have you felt, during the past 2 weeks, that life is not worth living? (sometimes or above)
- ii) Have you wished, during the past 2 weeks, that you were dead? For instance, that you could go to sleep and not wake up? (sometimes or above)
- iii) During the past 2 weeks, have you thought of taking your life, even if you would not really do it? (sometimes or above)
- iv) During the past 2 weeks, have you reached the point where you seriously considered taking your life or perhaps made plans how you would go about doing it? (rarely or above)
- v) Have you ever tried to take your own life? (yes)
- vi) When did you try to take your own life? (yes to any time selected)
- vii) Have you injured yourself on purpose in the past month? (yes)
- viii) Did you intend to experience pain or suffering as a result of your self-injury? (yes)
- ix) Did you intend to die as a result of your self-injury? (yes)

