### 5.6 Ancillary and post-trial care

As a duty of care mechanism, students who endorse any of the risk items (listed in section 4)

will be referred to their school wellbeing team for follow-up according to school welfare management protocol.

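### The confidentiality promise prescribed for the consent forms in section 2.2 has no exception for the section 4.3 referral of flagged students to the Principal, and only students are stated to be told of that referral

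*Protocol*

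**What the plan says.** Section 2.2 (Consent process) ends with a list of the information the consent forms will contain. One item covers confidentiality: data are to be held in strict confidence under privacy law, "used for health research only and will never be used in a way which would identify them personally". It has no qualifier for risk or duty of care. Another item in the same list is general: "The study methods and what participation would involve". The section also puts parental consent ahead of student consent.

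Section 4.3 describes what happens to completed surveys: "Student surveys will be confidentially viewed within 24 hours of completion by the research team as part of the monitoring and referral process". Nine items on suicidal ideation, attempts and self-harm trigger a flag. For flagged students, "the school Principal will be notified to coordinate follow up with these students", and the school's wellbeing team carries out the follow-up. The section adds: "Students will be notified of this referral process prior to them completing the questionnaire".

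Section 5.6 restates the arrangement as a duty-of-care mechanism: students who endorse a risk item "will be referred to their school wellbeing team for follow-up according to school welfare management protocol".

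Section 3.2 says surveys are stored under a study identifier, and that a password-protected file links identifiers to participant details.

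**The concern.** The section 2.2 statement uses two absolute terms: data serve health research *only*, and they are *never* used in an identifying way. The referral in sections 4.3 and 5.6 is neither confined to research nor anonymous. It is also not a remote contingency. It is a standing procedure applied to every survey, with a fixed review time and a fixed list of triggers.

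What is at stake is the quality of consent. The items concerned are the most sensitive in the survey, the participants are mostly minors, and a parent decides first. A parent or student who relies on an unqualified promise would not expect the school to learn that a particular child had been flagged. A form that carried both the promise and a description of the referral would contradict itself.

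**Working it through.** No arithmetic applies, since the point depends on no rate, effect size or sample size. The check is a comparison of the texts.

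1. **Is the use identifying?** Section 4.3 notifies the Principal so that particular students can be followed up. That cannot be done without saying who they are. The linking file in section 3.2 shows that a response can be traced to a named student. The use is therefore identifying. What section 4.3 implies is that the student's identity reaches the Principal; it does not say that the survey answers do.

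2. **Is the use research?** Section 5.6 describes the referral as a duty of care, and section 4.3 places follow-up with the school under its usual procedures. This is welfare work and falls outside a promise of research use only.

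3. **Could the promise be meant for publications only?** Anonymity in publications is stated separately in sections 3.2, 5.3 and 5.7. The section 2.2 sentence speaks of how data are *used* and is not limited to reporting.

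4. **Who is said to be told of the referral?**
   - Students: yes, before they complete the questionnaire (section 4.3).
   - The Principal: yes, prepared ahead of time (section 4.3). The introduction to section 4 also has the Principal and wellbeing team briefed on the survey's sensitive content.
   - Parents: no sentence says so. Section 2.2 says that they receive detailed information sheets about the program and the study, and section 2.1 allows for information sessions. Neither mentions the referral.

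5. **Does the notice to students close the gap?** Only in part. Section 2.2 has parents consent first. It also sends the downloadable parent form home so that students can reach a decision before the survey day. If that form follows the section 2.2 list, both would first decide on the unqualified statement, and the student would hear of the referral afterwards.

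6. **How far does it reach?** All enrolled students at all three surveys are covered by the promise. How many would be flagged cannot be calculated, because the protocol gives no expected frequency for any of the nine items.

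**The case against.** The strongest reply is that the section 2.2 list gives topics and is not the wording of the forms. The parent form, verbal script, student form and welfare protocol (Appendices E, G, H and K) appear only as file names. The item on study methods and what taking part involves could well carry a full account of the referral. The protocol does not say that parents are told, but neither does it say that they are not. This stands, and it limits the conclusion to what the plan prescribes. It does not remove the inconsistency, because a form that described the referral and also carried the section 2.2 promise would still say two incompatible things.

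Three stronger readings are tempting, and the documents do not support them.

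- *That consent rests on a false statement.* This is a claim about what parents and students actually read. The forms cannot be seen, and section 4.3 provides for notice to students before they answer.
- *That the item on individual feedback is also broken.* That item reads "That they will not receive any individual feedback about any aspect of their data". It concerns returning data to the participant. Section 4.3 notifies the Principal and returns no results to the student, so the two do not conflict.
- *That the primary outcome is biased, or that students will withdraw on discovering the referral.* Notice comes before the first questionnaire, so there is no later discovery to change reporting between waves. Section 1.5 has both arms surveyed at the same time under the same process, and nothing in the documents points to a difference between arms. Any under-reporting would come from the flagging itself, which a change of consent wording leaves as it is. Under section 2.2, data are destroyed on withdrawal only if the person refuses to let the study keep them.

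**Conclusion.** The inconsistency is real and should be corrected. Section 2.2 prescribes an absolute confidentiality statement; sections 4.3 and 5.6 require an identifying, non-research use of the same data; and the protocol states notice of that use to students but not to parents.

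This is a defect of consent wording. It changes no estimand, analysis or sample-size figure. It applies to every enrolled student, but the number whose identity would be passed on is unknown. The conclusion assumes that the forms follow the section 2.2 list. If the forms already qualify the promise and describe the referral to parents, what remains is a correction to the protocol text.

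**What to change.** Reconcile the confidentiality item in section 2.2 with sections 4.3 and 5.6, so that the promise made and the referral process agree. Then check that the parent form (Appendix E), the verbal script (Appendix G) and the student form (Appendix H) carry the same statement, and that parents receive it before they consent. The flag criteria and the referral rules need no change on account of this point.

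The cost is consent wording and an ethics amendment. Opt-in might fall slightly once the referral is stated to parents at the outset. The protocol gives no figure for this, so it is an assumption only.
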